8.2.2. Data Collection Forms

The data collection process consists of direct data entry at the study clinical centers into the EDC system(s) provided by the DCC. A data collection worksheet will be provided to clinical centers for recording data in the event the EDC system is unavailable. Data entry of the eCRFs should be completed according to the instructions provided and project specific training. The investigator is responsible for maintaining accurate, complete and up-to-date records, and for ensuring the completion of the eCRFs for each research participant.

8.2.3. Data Acquisition and Entry

Data entry into eCRFs shall be performed by authorized individuals. Selected eCRFs may also require the investigator's written signature or electronic signature, as appropriate. Electronic CRFs will be monitored for completeness, accuracy, and attention to detail during the study.

8.2.4. Data Center Responsibilities

The IPFnet DCC will 1) develop a data management plan and will conduct data management activities, 2) provide final eCRFs for the collection of all data required by the study, 3) develop data dictionaries for each eCRF that will comprehensively define each data element, 4) conduct ongoing data monitoring activities on study data, 5) monitor any preliminary analysis data cleanup activities, and 6) rigorously monitor final study data clean up.

8.2.5. Data Editing

Completed data will be entered into the IPFnet DCC automated data acquisition and management system. If incomplete or inaccurate data are found, a data clarification request will be generated and distributed to clinical centers for a response. Clinical centers will resolve data inconsistencies and errors and enter all corrections and changes into the IPFnet DCC automated data acquisition and management system.

8.2.6. Training

The training plan for clinical center staff includes provisions for training on assessments, eCRF completion guidelines, data management procedures, and the use of computerized systems.

9. Study Design and Data Analysis

9.1. General Analytic Considerations

All primary analyses will be based on intent-to-treat (ITT) principles using all randomized subjects. Baseline factors across groups will be compared using mean (standard deviation) and median (25th and 75th percentiles) summary measures. Kaplan-Meier curves will be used to display event rates. Due to clinical interest in departures from both sides of the null hypothesis, all test statistics will be 2-sided.

Reasonable caution needs to be taken when conducting multiple analyses on key clinical subgroups. For subgroup analyses, a conservative significance level of 0.001 will be used for all interaction tests. Thus, subgroup comparisons will be considered exploratory unless the p-value from the interaction test is smaller than 0.001.

9.2. Randomization, Blinding, and Reporting of Results

A permuted block-randomization scheme will be created with varying block sizes stratified by clinical center. Once a subject has completed the screening and baseline period and evaluation for inclusion/exclusion criteria, the randomization process will begin. Subjects will be randomized to receive NAC or matching placebo with equal probability (1:1), via telephone contact with a central interactive voice response system (IVRS), using a toll-free randomization number. On the day of randomization, after the subject has successfully met all inclusion and exclusion criteria, the investigator or designee will call the central randomization number to obtain the assigned kit randomization numbers for that subject. At each subject visit, the investigator or designee will call the central randomization number to obtain the new kit randomization numbers for resupply of the subject. For resupply of the clinical center, the IVRS will monitor minimal volume of a kit type and/or expiration date and will automatically notify the pharmacy.

The trial results will be reported according to guidelines specified in the CONSORT statement. A flow diagram describing screening, recruitment, randomization, dropout, and vital status will be included in the primary manuscript. AEs and efficacy data will be presented for all treatment groups. Adherence, dropout, and lost to follow-up will be carefully examined across all treatment groups. Analyses of safety will be based on data from all randomized subjects who received at least one dose of study drug.

9.3. Stratification

Subjects will be distributed to the two treatment arms in a 1:1 allocation ratio. Stratification blocks will be based on clinical centers.

9.4. Specification of the Primary Analyses

A mixed model repeated measures (MMRM) analysis, described in section 9.5, will be used to compare differences in the slope of FVC measurements across the treatment groups. Response variables are values of the FVC measured at baseline and every 15 weeks until study completion. Variables in the model will include: treatment, time, and time by treatment, age, sex, race, and height. Contrast estimates of differences in slopes of treatment over time (along with confidence intervals) will be used to estimate the treatment effect. The validity of this model in terms of meeting modeling assumptions will be assessed via standard modeling diagnostics and goodness-of-fit measures. Based on the MMRM framework, missing FVC data will not be imputed for the primary analysis.

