4.3. Exclusion Criteria

1. History of clinically significant environmental exposure known to cause pulmonary fibrosis.
Occupational exposures, such as asbestos, or environmental exposure to organic dust, such as occurs in pigeon breeders, may at times mimic the clinical and radiographic findings of IPF.
2. Diagnosis of connective tissue disease, felt by the principal investigator (PI) to be the etiology of the interstitial disease. Diagnosis of collagen-vascular conditions will be according to the published American College of Rheumatology criteria. As such, the presence of any documented collagen-vascular disorder or the presence of any suspicious symptom complex, whether or not associated with significantly abnormal rheumatological serologies, will exclude the subject, at the discretion of the PI.
3. Extent of emphysema greater than the extent of fibrotic change (honeycombing, reticular changes) on HRCT scan.
4. Forced expiratory volume in 1 second (FEV₁)/FVC ratio < 0.65 at screening (postbronchodilator).
5. Partial pressure of arterial oxygen (PaO₂) on room air < 55 mm Hg (< 50 mm Hg at Denver site).
6. Residual volume > 120% predicted at screening (postbronchodilator).
7. Evidence of active infection.
8. Significant bronchodilator response on screening spirometry, defined as a change in FEV₁ ≥ 12% and absolute change > 200 mL OR change in FVC ≥ 12% and absolute change > 200 mL. The percent difference between the FVC (or FEV₁) values will be calculated by taking the absolute value of the difference and dividing it by the larger of the two FVC (or FEV₁) values.
9. Screening and enrollment post-bronchodilator FVC measurements (in liters) differing by > 11%. The percent difference between the FVC values will be calculated by taking the absolute value of the difference and dividing it by the larger of the two FVC values (eg., the percent difference between FVC measurements of 1.9 and 2.0 liters would be determined by taking the difference between the two (0.1 liters) and dividing by the larger of the two (2.0 liters). So $0.1/2.0 = 5\%$, and these FVC measurements would not exclude the subject.
10. Listed for lung transplantation, i.e., the patient has completed the evaluation process, has been accepted as a candidate for transplantation at an appropriate center, and is waiting to receive notification of an available donor organ.
11. History of unstable or deteriorating cardiac disease.

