9.5. Analysis of Longitudinal Endpoints

A common goal in clinical trials is to specify models that are easily implemented and reproducible by independent data analysts. On the other hand, the models should have proper statistical behavior in terms of low bias and high precision. Many common approaches to longitudinal data analysis including last observation carried forward (LOCF) imputation rely on the missing completely at random (MCAR) assumption. However, the MCAR assumption is

unlikely to hold in many clinical trials because missing data are often related to disease progression and prognosis. A more reasonable assumption, missing at random (MAR), specifies that the complete data distribution can be modeled using only the observed data. The likelihood-based MMRM approach is valid under the more general MAR assumptions. These models will be applied to analyze the longitudinal data secondary endpoints.

The advantages of MMRM analysis are that all important characteristics of the model can be pre-specified, standard software can be used to implement the models, and results are based on ITT principles.⁴³ In addition, the MMRM approach offers superior control of Type I and Type II errors compared with the LOCF approach.

Response variables are values of the PFTs measured at enrollment and every 15 weeks until study completion and 6MWT values measured at baseline, week 30, and week 60. Covariates are treatment, time, time by treatment, and key baseline risk factors. Contrasts (along with confidence intervals) of treatment by time will be used to estimate the treatment effect.

The correlation structure involves multiple pieces, including measurement errors, random variation, and interindividual variability. For the longitudinal data analyses, an unstructured correlation matrix for within-subject errors will be assumed. Other correlation structures, including compound symmetry, will be examined as needed. A careful examination of reasons for study discontinuation will be conducted to assess the validity of MCAR. Sensitivity analyses will be used to examine the untestable assumption that the observed data violate the MAR assumption. The MMRM models will be implemented using PROC MIXED in SAS.

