9.7.2. Power Analysis for Secondary Endpoints

Power calculations for secondary endpoint measurements are shown in Table 7. Standard deviations are based on unpublished data provided by the University of Michigan. The calculations are based on a 2-sample t-test with Type I error rate set at 0.05. These calculations are likely to be conservative because the statistical approach, described in section 9.5, for analyzing these endpoints will incorporate incomplete observations as well as intermediate data points.

Table 7: Detectable Differences in Treatment Means for Selected Endpoint Measurements

Secondary Endpoints	Std Dev of the Baseline Score	Detectable Difference for 80% Power	Std Dev of the Change Score	Difference Detectable for 80% Power
DLCO%pred	16.6	5.8	9.1	3.2
6MWT Area Under the Desaturation Curve	21.9	7.6	17.5	6.1
6MWT Distance to Desaturation	22.4	7.8	31.5	11.0
6MWT Minutes Walked	2.10	0.73	2.05	0.71

Abbreviations: Std Dev, standard deviation; DLCO%pred, diffusing capacity of the lung for carbon monoxide percent predicted; 6MWT, 6-minute walk test

10. Study Administration

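### The longitudinal models leave each arm its own baseline mean; a common baseline mean would be a free but mostly modest gain in precision

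*Protocol*

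**What the plan says.** Protocol section 9.4 defines the primary response: "Response variables are values of the FVC measured at baseline and every 15 weeks until study completion". It then lists the terms: "Variables in the model will include: treatment, time, and time by treatment, age, sex, race, and height". The estimate is a slope difference: "Contrast estimates of differences in slopes of treatment over time (along with confidence intervals) will be used to estimate the treatment effect".

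Section 9.5 repeats the structure for the secondary longitudinal endpoints. The baseline value is again part of the response ("Response variables are values of the PFTs measured at enrollment and every 15 weeks until study completion", with the 6MWT at baseline, week 30 and week 60). The terms are given as "Covariates are treatment, time, time by treatment, and key baseline risk factors", and the effect is read from the interaction: "Contrasts (along with confidence intervals) of treatment by time will be used to estimate the treatment effect". An unstructured within-subject matrix is assumed.

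Neither section sets the arms' baseline means equal. Table 7 in section 9.7.2 gives an SD at baseline and an SD of change for four endpoints; for "6MWT Distance to Desaturation" these are 22.4 and 31.5.

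A second pre-randomisation FVC exists. Section 4.3 excludes subjects with "Screening and enrollment post-bronchodilator FVC measurements (in liters) differing by" more than 11%, so everyone enrolled has both values, but no model uses the screening one.

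**The concern.** Baseline is measured before treatment starts, and allocation is random and 1:1 (sections 9.2 and 9.3), so the expected baseline difference between arms is zero. A model with baseline in the response and an unrestricted treatment effect estimates that difference anyway. The treatment-by-time contrast then subtracts baseline in full instead of adjusting for it in proportion to its correlation with follow-up. Where that correlation is low, the subtraction adds noise.

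A common baseline mean avoids this and, in large samples, is never less precise. What is at stake is precision from data already collected. The validity of the comparison is not in question.

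**Working it through.** **1. Reproducing the 93% (section 9.7.1).** Inputs: variance 0.810, correlation 0.925, compound symmetry, 120 per arm after the compliance correction, visits at weeks 0, 15, 30, 45 and 60, slope difference 0.0025 L/week, two-sided 0.05, and 5% of the original sample lost after each visit (80% complete). From the generalised least squares information matrix with intercept, time, treatment and treatment by time, the SE of the slope difference is 0.000732.

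Power = Φ(0.0025/0.000732 − 1.96) = 92.7%. If the 5% is taken from those remaining, it is 93.0%. The stated figure reproduces. The covariates age, sex, race and height are left out.

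**2. Primary endpoint with a common baseline mean.** Omitting treatment at time 0 gives SE 0.000722, a variance ratio of 0.972 and power of 93.4%. The saving is 2.8%. It is small because the correlation is high.

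**3. Reproducing Table 7.** Detectable difference = (1.960 + 0.842) × SD × √(2/130) = 0.3475 × SD. For distance to desaturation this gives 7.78 and 10.95 (7.81 and 10.99 with the t distribution), against 7.8 and 11.0 in the table. All eight entries reproduce at 130 per arm.

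**4. Free versus common baseline mean, three visits, distance to desaturation.** With a free treatment effect, the contrast variance is 15.27 = 2 × 31.5²/130, exactly the change-score variance. With a common baseline mean it is 7.72. The ratio is 0.506.

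**5. All four endpoints, assuming follow-up SD equals baseline SD.** The implied correlation is ρ = 1 − SD_change²/(2 × SD_base²), and the variance ratio is (1 + ρ)/2.

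| Endpoint | SD base | SD change | ρ | Ratio | Saved | Detectable difference |
|---|---|---|---|---|---|---|
| DLCO%pred | 16.6 | 9.1 | 0.85 | 0.925 | 7.5% | 3.2 → 3.0 |
| Desaturation area | 21.9 | 17.5 | 0.68 | 0.840 | 16% | 6.1 → 5.6 |
| Distance to desaturation | 22.4 | 31.5 | 0.01 | 0.506 | 49% | 11.0 → 7.8 |
| Minutes walked | 2.10 | 2.05 | 0.52 | 0.762 | 24% | 0.71 → 0.62 |

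**6. Relaxing the equal-SD assumption.** With both table SDs held fixed, ρ = (SD_base² + SD_fu² − SD_change²)/(2 × SD_base × SD_fu), and the share saved is (SD_base − ρ × SD_fu)²/SD_change². This is a square, so it is never negative. For distance to desaturation:

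| SD_fu/SD_base | 0.8 | 0.9 | 1.0 | 1.1 | 1.2 | 1.3 | 1.4 | 1.5 | 1.7 |
|---|---|---|---|---|---|---|---|---|---|
| Saved | 69% | 59% | 49% | 39% | 30% | 21% | 13% | 7% | about 0% |

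At a ratio of 0.8 the other three save 36% (DLCO), 39% (area) and 45% (minutes). Each falls to about zero at a ratio between 1.1 and 1.4 and then rises again.

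**7. Baseline as covariate in 9.4.** If only weeks 15 to 60 stay in the response, baseline becomes a covariate and the slope contrast is kept, the SE is 0.001033. The variance ratio is 1.99 and power is about 68%.

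**8. Screening FVC.** Entered with its own mean common to both arms, and assumed to share correlation 0.925 under compound symmetry, it brings the variance ratio to 0.739 (26% saved in total, including the 2.8%) and power to 97.8%.

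**The case against.** The strongest reply is that section 9.4 contains no error. The slope contrast is unbiased under randomisation, the model is a standard one, the stated power is met, and the constraint moves it only from 92.7% to 93.4%. All of that stands.

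A reader might infer from Table 7 that half the variance for distance to desaturation is wasted. The table does not show this. It gives no follow-up SD, and a change SD of 1.4 times the baseline SD also fits a spread that widens over time, in which case little is lost. This is also one of many secondary endpoints, and section 9.7.2 presents the table as a conservative t-test approximation. That conservatism comes from intermediate and incomplete data, though, and does not remove the cost of a free baseline mean.

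A reader might also infer that leaving out screening FVC costs the primary analysis a quarter of its variance. That treats the screening value as exchangeable with later visits. The documents point the other way. It decides eligibility (section 4.1), is selected by the 11% agreement rule (section 4.3), may be an existing clinical test (section 4.4.2.1), may precede enrollment by up to eight weeks (section 4.4.2.2), and may be taken before a washout (sections 4.3 and 4.4.2.1). Using enrollment FVC as the only baseline is defensible.

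Finally, the baseline risk factors in 9.5 are unnamed, and section 10.4 leaves full detail to a SAP. This may soften the point for 9.5. It does not for 9.4, where the terms are listed.

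**Conclusion.** The point holds as a free improvement in efficiency. The models in 9.4 and 9.5 estimate a baseline difference that is zero in expectation, and equating the baseline means costs nothing. There is no bias and no shortfall against the stated 93%.

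For the primary endpoint the gain is about 3% of slope variance under the plan's own covariance. For the Table 7 endpoints it is about 7.5% to 49% if follow-up and baseline SDs are equal, which the protocol does not state. The direction is secure, because the saving cannot be negative in large samples. The size is not.

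The 26% from screening FVC holds only under compound symmetry with correlation 0.925. It is likely smaller given the agreement rule, washout and slopes that vary between subjects.

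**What to change.** In 9.4 and 9.5, keep baseline in the response vector and state that its mean is the same in both arms. With linear time, omit the treatment main effect at time 0 and keep treatment by time. With categorical visits, code treatment effects at post-baseline visits only; simply deleting the main effect while keeping the full interaction refits the same model in a different parameterisation.

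Baseline as covariate with follow-up values as response is an alternative only for visit-specific contrasts in 9.5. It should not be combined with the slope contrast in 9.4.

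Optionally, enter screening post-bronchodilator FVC in 9.4 as a further pre-randomisation observation with its own mean common to both arms, without relying on a particular gain.

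The cost is a few lines of model wording, with no new visits, subjects or data. It should be settled before the treatment comparison is seen; section 10.4 already places the SAP before database lock.

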9.5. Analysis of Longitudinal Endpoints

A common goal in clinical trials is to specify models that are easily implemented and reproducible by independent data analysts. On the other hand, the models should have proper statistical behavior in terms of low bias and high precision. Many common approaches to longitudinal data analysis including last observation carried forward (LOCF) imputation rely on the missing completely at random (MCAR) assumption. However, the MCAR assumption is

unlikely to hold in many clinical trials because missing data are often related to disease progression and prognosis. A more reasonable assumption, missing at random (MAR), specifies that the complete data distribution can be modeled using only the observed data. The likelihood-based MMRM approach is valid under the more general MAR assumptions. These models will be applied to analyze the longitudinal data secondary endpoints.

The advantages of MMRM analysis are that all important characteristics of the model can be pre-specified, standard software can be used to implement the models, and results are based on ITT principles.⁴³ In addition, the MMRM approach offers superior control of Type I and Type II errors compared with the LOCF approach.

Response variables are values of the PFTs measured at enrollment and every 15 weeks until study completion and 6MWT values measured at baseline, week 30, and week 60. Covariates are treatment, time, time by treatment, and key baseline risk factors. Contrasts (along with confidence intervals) of treatment by time will be used to estimate the treatment effect.

The correlation structure involves multiple pieces, including measurement errors, random variation, and interindividual variability. For the longitudinal data analyses, an unstructured correlation matrix for within-subject errors will be assumed. Other correlation structures, including compound symmetry, will be examined as needed. A careful examination of reasons for study discontinuation will be conducted to assess the validity of MCAR. Sensitivity analyses will be used to examine the untestable assumption that the observed data violate the MAR assumption. The MMRM models will be implemented using PROC MIXED in SAS.

9.6. Analysis of Binary, Time-to-Event, and Time-Lagged Endpoints

Regression modeling approaches using either the logistic regression model or Cox proportional hazards regression model will be employed when appropriate. The validity of these models will be assessed via standard modeling diagnostics and goodness-of-fit measures. Estimates of cumulative frequencies for more general time-lagged responses will be calculated using the partitioned version of the Bang-Tsiatis estimator.⁴⁴ The partitions will be set at 15-week intervals

to correspond with the data-collection process. Covariate adjusted event rates will be calculated using inverse probability-weighted regression estimates.⁴⁵

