4.4. Study Design and Study Visit

4.4.1. Study Design Summary

This study will be a randomized, double-blind, PL-controlled trial designed to assess the safety and efficacy of NAC in subjects with newly diagnosed IPF.

Subjects with mild to moderate IPF (defined as $FVC\%pred \geq 50\%$ and $DLCO\%pred \geq 30\%$) diagnosed within the past 48 months will be enrolled. Screening will continue until April 30, 2012.

The study will employ a 2-arm design with 1:1 randomization to NAC or PL. Once enrolled, subjects will visit the clinical center at 15 weeks and 15-week intervals thereafter. Each subject will be treated and followed for a maximum of 60 weeks.

During the 60-week visit, subjects will be taken off all study agents. Approximately four weeks after the final dose of study agent is taken, subjects will receive a safety phone call from the study site.

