4.4.2.9. Phone Contact Between Visits

At week 2 and each month that a subject does not have a scheduled clinical center visit, his or her study coordinator will contact him or her at least once by telephone to:

- Inquire if the subject has had any hospitalizations, events that might be considered an AE, or any events significant enough to warrant an out-of-cycle visit to the clinical center.
- Remind subjects of their current dosage levels and confirm that the subject understands them.
- Address any questions or concerns the subject might have regarding other aspects of the study.
- Assess adherence to the treatment regimen by reviewing diary data; verbal review of medications taken, including nutritional supplements.

Table 3: Schedule of Assessments

Procedure	Screening Visit 0	Enrollment Visit 1	Week 15 Visit 2	Week 30 Visit 3	Week 45 Visit 4	Week 60 / Early Withdrawal Visit 5	Final ¹ Visit (via phone)
Informed consent	X						
Medical history	X						
Inclusion/exclusion criteria	X						
Serum pregnancy test (if applicable)	X	X	X	X	X		
Review of lung biopsy	X						
Arterial Blood Gas	X					X	
6-Minute Walk Test				X		X	
Physical examination	X			X		X	
Vital signs with oximetry	X	X	X	X	X	X	
Body height and weight	X	X	X	X	X	X	
Complete Blood Count	X			X		X	
Chemistry panel	X			X		X	
Monitor Lab Values	X			X		X	
Urinalysis	X						
Specimen repository substudy blood draw and urine collection (if consented)			X	X	X	X	
HRCT (if not completed within three months)	X						
Spirometry (pre- and post-bronchodilator)	X						
Spirometry (post-bronchodilator only)		X	X	X	X	X	
DLCO (post-bronchodilator only)	X			X		X	
Lung volumes (post-bronchodilator only)	X						
Evaluate for acute exacerbation		X	X	X	X	X	
Review Adverse Events		X	X	X	X	X	X
Review concomitant meds	X	X	X	X	X	X	
Dispense subject diary		X	X	X	X		
Review subject diary		X	X	X	X	X	
Dispense study agent		X	X	X	X		
Gender Substudy questionnaire (female subjects only)		X					
EuroQoL, ICECAP, UCSD SOBQ, SGRQ, SF-36		X		X		X	

Abbreviations: DLCO, diffusing capacity of the lung for carbon monoxide; QoL, Quality of Life; ICECAP, Investigating Choice Experiments for Preferences of Older People; UCSD SOBQ, University of California Shortness of Breath Questionnaire; SGRQ, St. George's Respiratory Questionnaire; SF-36, Short Form 36 Health Survey

¹Follow-up visit via phone will occur four weeks after final dose of study medication

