5.2.2. Acute Exacerbations

The following 3 criteria will define AEx in subjects with acute worsening of their respiratory conditions:

1. Clinical (all of the following required):
 - A) Unexplained worsening of dyspnea or cough within 30 days, triggering unscheduled medical care (e.g., emergency room, clinic, study visit, hospitalization).
 - B) No clinical suspicion or overt evidence of cardiac event, pulmonary embolism, or deep venous thrombosis to explain acute worsening of dyspnea.
 - C) No pneumothorax.

2. Radiologic/Physiologic (A and B required):
 - A) New ground glass opacity or consolidation computed tomography (CT) scan, OR new alveolar opacities on chest x-ray.
 - B) Decline of $\geq 5\%$ in resting room air SpO₂ from last recorded level OR decline of ≥ 8 mm Hg in resting room air PaO₂ from last recorded level.

3. Microbiologic (all of the following required):
 - A) No clinical evidence for infection (i.e., absence of grossly purulent sputum, fever $> 39^{\circ}\text{C}$ orally).
 - B) Lack of positive microbiological results (if done) from lower respiratory tract defined as:
 - (1) Clinically significant bacterial growth on sputum or endotracheal aspirate cultures;
 - (2) Quantitative culture by protected brush specimen $\geq 10^3$ cfu/mL or BAL $\geq 10^4$ cfu/mL;
 - (3) The presence of specific pathogens on stains of any of the above.
 - C) Lack of positive pathogen in blood cultures (if done).

Identification of Acute Exacerbations

All subjects will be educated about the importance of identifying AExs. At the time of enrollment, subjects will be told about the possibility of developing acute symptomatic worsening that might represent an AEx of IPF, and instructed to contact their study clinical center coordinator within 48 to 72 hours of the apparent event.

All subjects will be contacted by phone monthly, and questioned about any change in dyspnea or cough and any interim clinic visits or hospitalizations. Finally, as part of the IPFnet outreach to community referring physicians, the importance of AExs will be emphasized. When a subject is identified who meets criterion 1A, this will trigger the collection of additional clinical data to evaluate a suspected AEx. These data will be collected as part of standard clinical care (i.e., this protocol does not require collection of all items). The additional items to be collected for suspected AEx include:

- IPFnet AEx case report form (eCRF) (required)

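### The 15-week partitions in section 9.6 are coarser than the collection of exacerbations and hospitalizations; if the estimator is meant for those endpoints, partitions of about 4 weeks are a free improvement

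*Protocol*

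**What the plan says.** Section 9.6 opens with regression: "Regression modeling approaches using either the logistic regression model or Cox proportional hazards regression model will be employed when appropriate". It then adds a second method: "Estimates of cumulative frequencies for more general time-lagged responses will be calculated using the partitioned version of the Bang-Tsiatis estimator". The width is fixed and justified in one sentence: "The partitions will be set at 15-week intervals" "to correspond with the data-collection process". The section does not list which endpoints count as time-lagged responses.

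On data collection, section 4.4.1 says that "subjects will visit the clinical center at 15 weeks and 15-week intervals thereafter". Between visits, section 4.4.2.9 adds telephone calls: "At week 2 and each month that a subject does not have a scheduled clinical center visit, his or her study coordinator will contact" the subject at least once, among other things to "Inquire if the subject has had any hospitalizations, events that might be considered an AE". Section 5.2.2 repeats this for exacerbations: "All subjects will be contacted by phone monthly, and questioned about any change in dyspnea or cough and any interim clinic visits or hospitalizations". Section 6.1.2.1 requires deaths and SAEs to be entered within 24 hours of the site learning of them. Section 4.4.2.6 provides a final visit at withdrawal, with AE and exacerbation review.

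**The concern.** In a partitioned estimator, a subject contributes to an interval only if followed to its end, or to death if that comes first. The wider the interval, the more recorded information is set aside when a subject is lost inside it. Take a subject hospitalized in week 20 who withdraws in week 26. With 15-week partitions, the interval from week 15 to week 30 is incomplete, so the hospitalization is left out of this estimate although it is in the database. With partitions of about 4 weeks, the interval containing week 20 is complete by week 26 and the event counts.

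The likely targets are the Aim 2 endpoints worded as frequencies: exacerbations, AEs, respiratory complications and hospitalizations. Section 9.5 sends the lung-function and walk-test measurements to the mixed model, and the frequency endpoints are the natural match for cumulative frequencies in 9.6. For these endpoints the stated reason for 15 weeks describes only part of the collection process. The stake is some efficiency and, if subjects tend to leave after an event, an underestimate that grows with the partition width.

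**Working it through.** **Estimator.** Let interval j end at b_j, let N_ij be subject i's events in it, C_i the time of loss, T_i the time of death, and K the estimated probability of remaining uncensored. Then

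frequency = (1/n) × sum over i and j of I(C_i ≥ min(b_j, T_i)) × N_ij / K(min(b_j, T_i)).

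A subject lost inside interval j adds nothing to interval j. Earlier complete intervals are kept, and so is an interval in which the subject dies.

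**Inputs from the protocol.** 60 weeks; 15-week width, so 4 partitions; about 130 subjects per arm; 5% lost after every visit and 80% followed throughout (9.7.1). The stated retention reproduces: 1 − 4 × 0.05 = 0.80 (compounding: 0.95^4 = 0.8145).

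**Inputs not in the protocol, assumed.** Event rates of 0.05, 0.10, 0.25 or 0.30 per subject over 60 weeks; the timing of loss; any link between events and loss. Monthly partitions are taken as 60/14 = 4.29 weeks.

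**1. Random loss, uniform in time, 20% lost.** Lost subjects are observed for 30 weeks on average, so mean observed time is 0.8 × 60 + 0.2 × 30 = 54.0 weeks. Each lost subject forfeits half an interval on average.
- 15-week: 0.2 × 7.5 = 1.50 weeks; 1.50/54.0 = 2.8%.
- Monthly: 0.2 × 2.14 = 0.43 weeks; 0.43/54.0 = 0.8%.

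Simulation (130 per arm, 4000 runs, between-subject variation in rate, no deaths) gives, per arm:

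| Rate | Events dropped, 15-week | Events dropped, monthly | SE, 15-week | SE, monthly |
|---|---|---|---|---|
| 0.05 | 0.15 | 0.04 | 0.0216 | 0.0214 |
| 0.10 | 0.32 | 0.09 | 0.0310 | 0.0308 |
| 0.30 | 0.97 | 0.27 | 0.0592 | 0.0585 |

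Neither width is biased, because the weights make up for the dropped intervals. A second simulation at rate 0.25 (400 runs) agrees: 2.9% against 0.8% of recorded events dropped, SE 0.0473 against 0.0468 (ratio 1.011).

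**2. Loss directly after a visit, as 9.7.1 words it.** The 15-week partitions drop 0%. A 4.29-week grid, whose cut points mostly miss the visit times, drops about 0.4%.

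**3. Loss that follows events.** Assumption: loss hazard multiplied by 5 or 10 for 12 weeks after an event, rate 0.25, background weekly hazard about 0.0024 to 0.0037, 400 runs.

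| Multiplier | Events dropped, 15-week / monthly | Estimate ÷ truth, 15-week / monthly |
|---|---|---|
| 1 | 2.9% / 0.8% | 1.00 / 1.00 |
| 5 | 9.9% / 2.9% | 0.92 / 0.975 |
| 10 | 15.6% / 4.1% | 0.86 / 0.96 |

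The frequency is thus 8-14% too low against 2.5-4% too low. Monte Carlo error on each mean is roughly 1% (0.0473/√400 = 0.0024, relative to 0.25). A repeat of the simulation gave about 8% and 13% against 3% and 4%.

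A harsher assumption is 15% background loss plus a 20% or 50% chance that an event leads to loss within 4 weeks. At a true rate of 0.10, the 15-week partitions then estimate 0.082 or 0.056, and the monthly ones 0.089 or 0.072. The direction is the same, and the monthly estimate is still clearly low.

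**The case against.** A reader might infer that the plan throws away recorded exacerbations and hospitalizations, or that 15 weeks contradicts the protocol's own data collection. The documents support neither.

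- Section 9.6 never assigns these endpoints to the estimator. The link is a reasonable inference, no more.
- Table 3 lists exacerbation evaluation and AE review at every 15-week visit. The reason given for the width is therefore incomplete rather than false.
- Only one cumulative-frequency estimate is touched. Cox and logistic models do not use partitions, and safety reporting covers all recorded events.
- Under random loss the weighting compensates, and the difference between the widths is less than one event per arm at the assumed rates.
- The 8-14% figure needs loss that depends on events. That breaks the estimator's censoring assumption, and finer partitions do not cure it. Neither the multiplier nor the 12 weeks comes from the protocol.
- The protocol works against such loss: subjects stay in the study during a suspected exacerbation (5.2.2), and those who stop study drug are encouraged to complete all visits (4.5).

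All of this stands and keeps the point small. It does not remove it. Section 9.5 itself expects missing data to be related to progression and prognosis, and section 5.2.2 foresees subjects too frail to return after a suspected exacerbation, so event-related loss is plausible. Section 10.4 leaves full analysis detail to the SAP, but the width is already fixed in the protocol, so it can be reviewed here.

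**Conclusion.** The point holds as a minor one on secondary endpoints, conditional on the estimator being used for the frequency endpoints. In that case 15 weeks is coarser than the data allow. With random loss the price is about 1% in standard error and no bias, and it falls to nothing if loss comes right after a visit. With event-driven loss the wider partitions underestimate more: about 8-14% against 2.5-4% low under the assumed 5- to 10-fold hazard. That range shows sensitivity and is not a prediction for this trial. No effect on the comparison between arms has been shown. An equal proportional shortfall in both arms would leave the ratio of frequencies unchanged and shrink their difference by the same proportion.

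**What to change.** In section 9.6, name the endpoints that use the partitioned estimator. For those collected by telephone or continuously (exacerbations, respiratory complications, hospitalizations, AEs, if these are intended), set partitions of about 4 weeks. Cut points that include the visit times avoid the small loss seen in step 2; for example, 15/4 = 3.75 weeks gives 16 partitions over 60 weeks. Keep 15 weeks for quantities measured only at clinic visits.

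The cost is a sentence or two in the protocol or SAP and one programming parameter, settled before database lock. The monthly contacts and event reporting are already planned, so no new data collection is needed. The change lessens bias from event-driven loss but does not remove it.
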